3.8 Safety Analysis

All adverse events (AE) will be reported using System Organ Class (SOC) classification. The proportion of subjects experience each AE along with the mean(SD) duration will also be reported. The reporting may be done stratified by disease group and/or site if required.

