- Prevalence of impaired swallowing safety and efficiency of the swallows of thin (THIN-Ba) and thickened stimuli as determined by VFSS at bolus and patient level by the following predetermined subgroups: stroke, other neurological diseases, other patients.
- Timing and Outcome of the dysphagia screening as per usual care protocol of the study site
- Timing and Outcome of the dysphagia Clinical Swallow Assessment (CSE) by SLP (speech language pathologist) where applicable as per usual care protocol of the study site
- Impact of VFSS results on Nutritional Management
- DDS accuracy in terms of AUC, sensitivity and specificity by sub-group (Stroke, Other Neurological Diseases and Others) for swallow safety and efficiency problems for all consistencies (THIN-Ba, MILD-Ba, MOD-Ba)

Safety Endpoints

All adverse events (AEs) will be observed during and within two business days following the study procedure.

TRIAL DESIGN

An operationally seamless single-arm, prospective, multicenter, single-blinded for central outcomes assessors trial to test DDS in assessing swallowing safety and efficiency in patients at risk of oropharyngeal dysphagia. The study is designed as operationally seamless to facilitate the updating of the threshold on the ROC curve for swallowing safety if required and to validate the DDS classifier with a fixed threshold using an independent validation set.

The study has been planned to enroll and study approximately 900 patients (maximum enrollment 1300) with the possibility of early stopping for futility or success.

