12.7 Post-Exam

After completion of all study-related testing, the site will stop the recording on the study computer and follow specified procedures for saving and uploading all study files to a secure transmission to the CRO as per the Study Manual.

Subsequently, the site will follow their institution's standard of care for further assessing swallowing impairment in subjects with suspected dysphagia.

Follow-up with the study subject will be performed within 2 business days following completion of all the exams to collect data on AEs. If the subject is still hospitalized at this time, this data will be collected via an in-person interview. If the subject has been discharged at the time of follow-up, this data will be collected via a telephone interview.

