15.1 Definitions and assessment criteria

15.1.1 Adverse event

An AE is any untoward medical occurrence experienced by a subject during this trial regardless of its relationship to the device.

All AEs (regardless of suspected causality) will be assessed from the time the Informed Consent Form is signed through the exit of the subject from the study.

All AEs will be assessed by the Investigator according to:

- Whether the event is an unanticipated adverse device effect (UADE);
- Whether the event is serious (SAE);
- The severity of the event (mild, moderate, severe); and
- The relationship of the event to the device and/or procedure (not related, possibly related, probably related, or definitely related).

Information will also be collected on any treatment of the event and outcome/resolution status of the event. All data concerning AEs will be recorded on the AE CRF.

All SAEs and UADEs will be reviewed by a Nestlé Health Science Medical Safety Officer (MSO). The MSO's decisions regarding SAE status and device- or procedure-relatedness will be considered final for the purposes of data analysis, regulatory reporting, and publications.

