15.2.2 Follow up of serious adverse events

All SAEs and UADEs must be followed up until the outcome is resolved or stable.

In case of SAE(s) persisting beyond trial termination, a follow up visit may be required. If further analyses are required for the evaluation of a potential cause-effect relationship between the device and the AE, all examinations and laboratory analyses will be documented in the (e)CRF or in an attached file.

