2.5 Safety Endpoints

All adverse events (AEs) will be observed from the time the consent form is signed through the exit of the subject from the study.

3 Statistical methodology

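### SAP 3.8 plans a plain mean (SD) duration for each AE, but non-serious AEs after the procedure are seen only to one contact within 2 business days, and no rule covers events still ongoing at exit

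*SAP*

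**What the plan says.** SAP 3.8 covers all adverse events: "All adverse events (AE) will be reported using System Organ Class (SOC) classification". It then adds: "The proportion of subjects experience each AE along with the mean(SD) duration will also be reported". It gives no rule for an event that has not ended when the subject leaves the study, and SAP 3.10.3 on missing data deals only with VFSS labels and device output.

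Protocol 12.7 sets the only scheduled AE contact after the exams: "Follow-up with the study subject will be performed within 2 business days following completion of all the exams to collect data on AEs". The contact is in person or by telephone, and none is scheduled later.

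Follow-up beyond that point is required for one class only. Protocol 15.2.2 says: "All SAEs and UADEs must be followed up until the outcome is resolved or stable". For AEs in general, Protocol 15.1.1 says: "Information will also be collected on any treatment of the event and outcome/resolution status of the event". That records whether an event has resolved but does not require the site to follow it until it does.

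The AE window opens before the exam. Protocol 15.1.1 has: "All AEs (regardless of suspected causality) will be assessed from the time the Informed Consent Form is signed through the exit of the subject". SAP 2.5 agrees: "All adverse events (AEs) will be observed from the time the consent form is signed through the exit of the subject from the study". The synopsis allows consent up to 2 weeks before the procedure, yet its safety endpoint is narrower: "All adverse events (AEs) will be observed during and within two business days following the study procedure".

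**The concern.** A mean and SD need a start and an end for every event. For a post-procedure AE that is neither an SAE nor a UADE, the end is recorded only if it falls before the contact or if a site happens to obtain it later. A programmer working from SAP 3.8 as written would have to leave out the ongoing events, which keeps the short ones, or give them the contact date as an end date, which shortens the long ones. Both push the mean down, and the SD is compressed for the same reason.

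Pooling makes the figure harder to read. Within one AE term, the mean could combine SAEs followed to resolution, post-procedure events cut off after a few days, and events that began up to 2 weeks before the exam. The result would depend on the mix of those groups and on when each site made its contact. Several anticipated events listed in Protocol 15.1.4, such as fever, respiratory infection, constipation and a skin reaction to the adhesive, could outlast the window and would then look briefer than they were.

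**Working it through.** The documents state no AE duration, so there is no figure of the plan's own to reproduce. The check has two steps.

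**1. How long an event can be observed**

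Inputs: one contact within 2 business days (Protocol 12.7); collection from consent (Protocol 15.1.1, SAP 2.5); consent up to 14 days before the procedure (Protocol synopsis). I assume a weekday procedure, no public holiday, and contact at the latest permitted time.

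- Exam on Monday, Tuesday or Wednesday: the second business day is 2 calendar days later.
- Exam on Thursday or Friday: the weekend intervenes, so it is 4 calendar days later.
- Non-serious AE starting on or after the procedure: at most 2 to 4 days.
- Non-serious AE starting just after consent: at most 14 + 2 = 16 to 14 + 4 = 18 days.
- SAE or UADE: no fixed limit, because follow-up runs until resolved or stable.

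A contact made sooner than the limit, or an onset later than the exam, shortens the first of these windows further.

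**2. Illustration of the bias**

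Assumptions, none of them from the documents: exponential durations with true mean m, onset at the start of a window of w days.

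- Share ongoing at contact: exp(−w/m)
- Mean of resolved events only: [m − (w + m)·exp(−w/m)] / [1 − exp(−w/m)]
- Mean with the contact date as end date: m·[1 − exp(−w/m)]

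Worked case, m = 7 and w = 2: exp(−2/7) = 0.751. Resolved only: (7 − 9 × 0.7515)/0.2485 = 0.95. Cut at contact: 7 × 0.2485 = 1.74.

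| True mean m (days) | Window w (days) | Ongoing | Mean, resolved only (days) | Mean, cut at contact (days) |
|---|---|---|---|---|
| 2 | 2 | 37% | 0.84 | 1.26 |
| 2 | 4 | 14% | 1.37 | 1.73 |
| 5 | 2 | 67% | 0.93 | 1.65 |
| 5 | 4 | 45% | 1.74 | 2.75 |
| 7 | 2 | 75% | 0.95 | 1.74 |
| 7 | 4 | 56% | 1.81 | 3.05 |
| 5 | 16 | 4% | 4.32 | 4.80 |
| 5 | 18 | 3% | 4.49 | 4.86 |

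The last two rows show the contrast for events that begin just after consent: with the longer window, a true mean of 5 days is nearly recovered. With the 2-day window the resolved-only mean stays between 0.84 and 0.95 while the true mean rises from 2 to 7, so it carries almost no information about the true duration.

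**The case against.** A reader might infer that every duration reported under SAP 3.8 is capped at a few days by construction. The documents do not support that. SAEs and UADEs have no fixed limit. Collection opens at consent, so a non-serious AE can show 16 to 18 days. No passage makes the contact date the end date, and a site may obtain a later one. The short limit applies only to post-procedure AEs that are neither SAEs nor UADEs.

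Nor does it follow that duration cannot be analysed at all. Resolution status is collected for every AE, so ongoing events can be identified and treated as censored. The fault lies in a plain mean with no rule for those events.

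It would also go too far to say that the safety profile of the device is understated. Incidence, severity and relatedness do not depend on duration. A respiratory infection that leads to or prolongs hospitalisation can meet the SAE definition and would then be followed up. Protocol 15.1.4 attributes the anticipated events to underlying disease as well as to the tests.

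Finally, the safety tables listed in SAP 3.12.6 contain no duration table, so the summary rests on one sentence in 3.8, and no test, threshold or stopping rule uses it. The 2-, 5- and 7-day means and the exponential shape are assumptions.

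All of this stands and limits the point. It does not remove it: 3.8 still names a statistic which, on the data the protocol requires, is biased short for one identifiable group of events under either obvious handling.

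**Conclusion.** The point holds for post-procedure AEs that are neither SAEs nor UADEs. They are observed for about 2 to 4 calendar days, with no required follow-up to resolution and no rule for events ongoing at exit. Their mean duration is biased short whether ongoing events are dropped or cut at contact, and pooling with the other two groups makes the combined mean hard to interpret.

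The direction of the bias follows from the follow-up schedule, provided some events outlast the contact and later end dates are not obtained. The size does not, because the documents give no durations. Under the assumed exponential with a true mean of 7 days, 56 to 75% of events are ongoing and the reported mean is about 1.0 to 1.8 days (resolved only) or 1.7 to 3.0 days (cut at contact). With a true mean of 2 days the loss is smaller: 14 to 37% ongoing, and a reported mean of 0.8 to 1.7 days across the two methods.

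This is a minor correction to a descriptive safety line.

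**What to change.** In SAP 3.8, replace the mean (SD) duration with the number of events resolved and the number ongoing at exit for each AE, taken from the outcome status already on the AE form.

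If a duration is kept, treat ongoing events as censored at last contact, for example with a Kaplan-Meier summary, and show SAEs and UADEs separately. The median may not be reached for post-procedure events: in the 7-day illustration more than half are still ongoing when the window closes. The counts are therefore the safer default.

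Bring 3.8 into line with the table list in 3.12.6. At the same time, reconcile the passages that define the window: the synopsis against Protocol 15.1.1 and SAP 2.5 on when AE observation starts; Protocol 12.6, which speaks of a 1 day follow-up visit, against the 2 business days in 12.7; and the unfilled XX days in the treatment-emergent definition in SAP 3.12.6.

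The cost is SAP wording and one table shell, with no new data. The downside is that a single mean duration is no longer shown.

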3.9 Analysis Sets

3.9.1 Full Analysis Set (FAS)

The FAS is based on a modified-intent-to-treat ppulation which is defines as all subjects with a signed informed consent and at least one analyzable swallow with the Thin-BA boluses using the VFSS.

3.9.2 Per Protocol Set (PPS)

PPS includes all subjects in the FAS except for those who are excluded because of major protocol deviations. Final determinations of the major protocol deviations will be made and documented separately prior to database lock.

3.9.3 Safety Analysis Set

This consists of all subjects who have completed at least one swallow.

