14.8.2 Safety analysis set

Safety population includes all subjects with documented VFSS exam.

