15.1.4 Anticipated Adverse Events

AEs that are anticipated to occur during this clinical trial are believed to be consistent with those associated with underlying disease and/or dysphagia screening tests and VFSS or have been identified by the Sponsor as part of their risk assessment. Anticipated AEs include and are not limited to, the following:

- Choking episode or airway obstruction event requiring emergency response
- Fever
- · Congestion and/or shortness of breath
- Chest pain
- Anaphylactic reaction (allergy to the test stimuli)
- New diagnosis of respiratory infection
- Nausea and/or Constipation

Potential AEs that may be specifically related to the investigational device (accelerometry device) include, but are not limited to, the following:

- Allergy, skin reaction, or irritation to the adhesive used for the sensor fixation
- Infection
- Discomfort
- Electrical shock
- Electromagnetic (EM) emission interference with other devices leads to failure of life supporting device*

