Procedure-related Adverse Event: an AE is considered to be procedure-related when, in the judgment of the Investigator or the MSO, it is reasonable to believe that the event is associated with the procedure and is not specific to the device. Other products, surgical techniques, or medications required specifically for the procedure are likely to have contributed to the occurrence of the event.

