3.12.6 Safety Analysis

All safety analysis will be performed on the Safety Analysis Set. All adverse Events (AEs) will be coded using the Medical Dicotionary for Regulatory Agencies (MedDRA). A TEAE is defined as an AE that starts or worsens on or after study Day 1 (defined as the procedure day), and no more than XX days after the procedure. All TEAEs will be listed by subject number and MedDRA coding.

The number and percentage of subjects with TEAE will be summarized in several different tables:

- All TEATs by System Organ Class (SOC) and preferred term (PT)
- Study procedure related AEs by SOC and PT
- Severity of All TEAEs by SOC and PT.

A subject with 2 or more AEs within the same level of the MedDRA term will be counted only once in that level using the most extreme incident (most severe for the severity table and related for the relationship to study procedure table).

4 Blinding and Firewall for Interim Analysis

The key blinding required for this trial is the blinding of the sites to the VFSS results determined by a central VFSS laboratory and the blinding of the central VFSS laboratory to the yet-to-be validated results from the DDS available at the sites. There will be no communication between the sites and the central laboratory. The results of the VFSS on each subjects' boluses will be kept blinded and would not be available to the sites or the sponsors. It will be made available to the iDMC and the iSC members with the unblinded role through a secured firewall system immediately prior to the time of the interim and the final analyses. The details will be pre-specified in the study protocol as well as in the DMC charter.

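### The SAP safety set requires a completed swallow, which conflicts with the protocol and omits events before that point, and no planned table shows device-related adverse events separately

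*SAP*

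**What the plan says.** The two documents define the safety population differently.

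- SAP 3.9.3: "This consists of all subjects who have completed at least one swallow".
- Protocol 14.8.2: "Safety population includes all subjects with documented VFSS exam".

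SAP 3.12.6 applies the SAP definition throughout: "All safety analysis will be performed on the Safety Analysis Set". It plans three tables: all TEAEs, AEs related to the study procedure ("Study procedure related AEs by SOC and PT"), and TEAE severity. It adds a listing: "All TEAEs will be listed by subject number and MedDRA coding".

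Protocol 15.1.1 has the investigator grade each AE for relationship to the device and/or the procedure. Protocol 15.1.6 defines device-related and procedure-related events separately, and an event is procedure-related when "it is reasonable to believe that the event is associated with the procedure and is not specific to the device". Protocol 15.1.4 names potential device events, the first being "Allergy, skin reaction, or irritation to the adhesive used for the sensor fixation".

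**The concern.** A safety set should be fixed by exposure, so that having an event cannot remove a subject from it. In this trial exposure begins when the sensor goes on the neck and continues when the first bolus is offered. A completed swallow comes after both. Under the SAP rule, an event in that interval that ends the exam also removes the subject from the set used to describe safety. Any resulting bias runs towards fewer reported events.

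The second part concerns attribution. A trial meant to validate a device should let the reader see which adverse events were attributed to it. As listed, the SAP tables do not show this separately from the barium and fluoroscopy procedure.

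**Working it through.** No formula applies and the plan gives no figure to reproduce. The check is a comparison of the texts.

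**Step 1: order of exposure.** Protocol 11.1 has the sensor attached to the front of the neck by an adhesive fixation. Protocol 12.5 has DDS and VFSS recorded simultaneously for the same bolus. The sensor is therefore in place before the first swallow. Protocol 12.6 lets the investigator stop at any time, so an exam can end before any swallow is completed.

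**Step 2: who is counted under each definition.**

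| Situation | Protocol 14.8.2 | SAP 3.9.3 | Exposure-based set |
|---|---|---|---|
| Sensor reaction before fluoroscopy, exam abandoned | Probably out (no VFSS exam to document) | Out | In |
| Exam recorded, event at first bolus, swallow not counted as completed | In | Out | In |
| First bolus swallowed, aspiration, exam then stopped | In | In | In |
| Sensor reaction after at least one completed swallow | In | In | In |

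The two definitions disagree in the second row, and both probably miss the first. SAP 3.9.3 names no consistency, so a completed swallow of any of the three is enough to be counted. Neither document says what makes a swallow completed, so the line between the second and third rows is left to judgement.

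**Step 3: whether another rule already excludes these events.** SAP 3.12.6 starts the TEAE window on the procedure day. A reaction when the sensor is applied that day is inside the window. The exclusion therefore comes from set membership alone.

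**Step 4: how many subjects.** The documents give no rate of exams ending before a completed swallow. Purely as an assumption, take 0.5% to 2%:

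- At the planned 900 subjects: 900 × 0.005 = 4.5 and 900 × 0.02 = 18, so about 5 to 18 subjects.
- At the maximum of 1300: 1300 × 0.005 = 6.5 and 1300 × 0.02 = 26, so about 7 to 26 subjects.

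These are subjects outside the set, not events. The number with an adverse event would be the same or smaller.

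**Step 5: relatedness.** Protocol 15.1.1 collects relatedness to device and/or procedure, and Protocol 15.1.6 separates the two. The relatedness table in SAP 3.12.6 is for the procedure only, and the counting rule in that section likewise mentions only relationship to study procedure. The listing it describes gives subject number and MedDRA coding, not relatedness. There are two possible readings:

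- Under Protocol 15.1.6, device-specific events are not procedure-related, so they appear in no relatedness table.
- The protocol synopsis uses study procedure for simultaneous VFSS and DDS measurement. On that reading device events are in the table, pooled with barium and VFSS events.

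Under neither reading can device-related events be read off by themselves.

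**The case against.** The strongest reply is that little is lost. AEs are recorded on the eCRF from consent (Protocol 15). SAEs and UADEs are entered within 24 hours and reviewed (Protocol 15.1.1 and 15.2.1), and UADE evaluations go to FDA and the IRBs (Protocol 15.3). SAP 3.8 says all AEs will be reported, without naming a set. The iDMC sees AE data at the interims (SAP 3.11.3), and early terminations are tabulated with reasons (SAP 3.12.1). No efficacy endpoint or decision rule is touched, and SAP 3.11.3 records the device as deemed Non-Significant Risk. All of this stands and limits the point to the planned safety tables. It does not reconcile the two definitions, and SAP 3.12.6 is the section that supplies the analysis population.

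A reader might infer more than the documents support:

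- **That any sensor reaction or first-bolus event that ends the exam drops out.** It does so only if no swallow was completed.
- **That excluded events go unreported.** They leave the tables, not the record.
- **That the trial cannot state a device-related AE rate.** Device relatedness is collected for every AE, and SAP section 1 allows supplementary analyses identified in the CSR. The table is unplanned, not impossible.
- **That near-zero counts are expected, so one lost event is decisive.** Protocol 16.3 reports no *serious* related events in more than 300 Phase 0 subjects. Adhesive reactions and discomfort need not be serious, and no rate is given for them. With 900 subjects, the one-sided 95% upper limit is 1 − 0.05^(1/900) = 0.33% for no events and about 4.74/900 = 0.53% for one. That shows the leverage of one event, not the size of the defect, and the SAP sets no AE limit that the difference would cross.

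**Conclusion.** The point holds within these limits. The SAP and protocol safety sets conflict, and the SAP version makes membership depend on something that happens after exposure starts. The effect is confined to subjects with no completed swallow, whose number is unknown and probably small. The direction, where there is any effect, is towards fewer tabulated events. The absence of a separate device-related table holds under either reading of study procedure.

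This rests on taking SAP 3.12.6 literally when it puts all safety analysis on the SAP set, and on the sensor being in place before the first swallow. The sponsor should correct it, but it does not threaten the trial's main conclusions.

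**What to change.** 1. Put one safety-set definition in SAP 3.9.3 and Protocol 14.8.2: all subjects in whom the sensor was applied or the swallow exam was started, whether or not a swallow was completed. Simply adopting the existing protocol wording would remove the conflict, but could still miss a sensor reaction before fluoroscopy.
2. In SAP 3.12.6, add a table of device-related AEs by SOC and PT beside the procedure-related one, using the relatedness already assessed for each AE. State that the two follow the definitions in Protocol 15.1.6.

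**Cost.** The protocol needs a matching wording change as well as the SAP. The sponsor must confirm that sensor application or exam start is recorded for subjects without a swallow, since the baseline data listed in Protocol 12.3 include neither. There is one extra table. The denominator may rise by a few subjects, and the AE rate may look slightly less favourable.
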